4.0 OBJECTIVES

4.1 Primary objective

The primary objective of the single arm phase II trial is to determine whether the surgery feasibility rate of neoadjuvant pembrolizumab is not significantly worse than the historical surgical feasibility rate of neoadjuvant chemotherapy. Surgery feasibility rate of a neoadjuvant therapy is the percent of

20

The information contained in this document is regarded as confidential, and may not be disclosed to another party unless such disclosure is required to initiate the study, to conduct study-related activities, or to comply with national, state, or local laws and regulations. Written authorization from the coordinating site and sponsor is required for disclosure otherwise.

11 Nov 2018

patients who are able to undertake surgery after the neoadjuvant therapy. A total of 30 eligible patients will be registered to the single arm trial. Taking 5% rate of cancellation and ineligibility into account, the trial will enroll a total of 32 patients and eligible subjects (not screen failures) will be followed for 2 years for both disease recurrence and death.

Primary Objective Sample Size Justification

According to Pisters et al (JCO 2010), approximately 80% of subjects undergo surgical exploration within 42 days of day 1 of the last cycle of standard neoadjuvant chemotherapy. We would like to test the following hypotheses:

$$H_0: p \geq 0.80 \text{ vs. } H_a: p < 0.65$$

where p is the true surgery feasibility rates after neoadjuvant pembrolizumab. With 30 evaluable patients receiving protocol treatment, the study has approximately 84.6% power rejecting $H_0: p \geq 0.80$ when $p=0.65$ at one-sided significance level of 15%.

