5.0 STUDY PLAN /DESIGN

Standard diagnostic and staging work up will be performed prior to or during surgery according to institutional standard practice including: pathologic/histologic diagnosis of non-small cell lung cancer, PET/CT scan, brain imaging, and if clinically indicated, mediastinoscopy. Two doses of neoadjuvant pembrolizumab will be given. Standard surgical evaluation and surgery will be performed following completion of 2 cycles of neoadjuvant pembrolizumab therapy.

After surgery, patients who are appropriate candidates will receive adjuvant chemotherapy, adjuvant radiation, and follow-up as per standard of care and institutional best practice. After all standard therapy, patients will receive 4 additional cycles of pembrolizumab every 21 days for 4 cycles. Patients who are not candidates for adjuvant therapy or who refuse may receive four cycles of adjuvant pembrolizumab.

All post-surgical therapy is as per institutional standard of care and is not study specific. Post-surgery chemotherapy, radiation may be given through the patient's primary oncology team as per the wishes of the patient. This allows a patient to have neoadjuvant pembrolizumab and surgery at an institution participating in this study, receive standard chemotherapy and radiation therapy near home, and return to the institution participating in the study to receive adjuvant pembrolizumab. Patients will be seen for a visit approximately 30 days after the last dose of pembrolizumab and follow-up will continue until pembrolizumab related side effects are grade 1, or Investigator deems stable. Patients will be followed for outcome for up to 7 years. Long term outcome data may be collected by phone.

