9.8.5 End of Study Visit (*Safety Follow-up)

End of study evaluation is to occur approximately 30 days or more after last adjuvant Pembrolizumab treatment.

- Vital signs (temp, B/P, pulse)
- Weight
- Performance status
- Physical exam
- Routine blood work
- Thyroid functions (T3, FT4, & TSH)
- Adverse events assessment
- Chest CT if applicable (per radiologic evaluation appendix A)
- Research blood (4th Collection): blood will be collected to assess longitudinal analyses of T cell and MDSC phenotypes and blood based biomarkers. 4 tubes of 8.5-ml each will be collected. The tubes used will be ACD anti-coagulated Vacutainer (yellow tops). Samples will be collected, and transported/shipped to the Substrate Services Core lab for processing (Refer to Appendices F & G).

*All AEs that occur prior to the Safety Follow-Up Visit should be recorded. Subjects with an AE of Grade $>$ 1 related to Pembrolizumab will be followed until the resolution of the AE to Grade 0-1, or investigator deems stable, or until the beginning of a new anti-neoplastic therapy, whichever occurs first. SAEs that occur within 90 days of the end of treatment or before initiation of a new anti-cancer treatment should also be followed and recorded.

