9.8.6 Follow-up

Patients should have follow-up as per standard care of the treating institution. Outcome data (recurrence and survival) will be collected every 3-4 months for 2 years after surgery. Following that, collect follow-up every 6 months for up to five years. Follow-up can occur by primary oncology provider and data can be collected by phone.

Every effort should be made to collect information regarding disease status during this follow-up which may include the start of new anti-neoplastic therapy, disease progression, death, end of the study.

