- 1) Whether the cumulative percentage of deaths among all treated patients related to any of the study treatments from the first pembrolizumab treatment until 30 days after surgery exceeds 17%.
- 2) If the cumulative percentage of all treated patients deemed unable to go to surgery due to adverse events attributed to neoadjuvant therapy exceeds 20%. The percentage of patients unable to go to surgery after pembrolizumab is a conservative estimate based on data reported for a SWOG trial that studied neoadjuvant chemotherapy in early stage lung cancer (22).

The first 10 treated patients will be evaluated for safety and feasibility. If in the first ten patients the criteria for overall therapy being not safe or feasible is met, accrual to the study will be suspended to allow for investigation. After consideration by the study team and the IRB, a decision will be made as to whether accrual can be resumed, potentially with modifications to entry criteria and/or study conduct. In addition, all toxicity patterns will be monitored by the DCI Safety Oversight Committee.

The trial will be stopped for accrual whenever a total of 35 patients are registered or at least one of the thresholds of the safety and feasibility criteria is exceeded. In the event either of these two thresholds is exceeded, the investigational therapy will be considered “infeasible” in this setting.

Accrual and follow-up

With an expected rate of 2 patients being enrolled each month, the trial will take about 16 months to reach the target accrual. All registered patients will be followed for tumor response, disease free survival and overall survival.

Statistical Analysis Plan

Surgery feasibility rate, the primary endpoint of the trial, will be analyzed using the data from all evaluable patients, who are defined as the patients who meet eligibility criteria and has received at least 1 dose of pembrolizumab. The surgery feasibility rate of neoadjuvant pembrolizumab as well as its confidence interval will be estimated.

Secondary Objectives

All secondary objectives are considered exploratory in nature, and type I error will not be controlled for multiplicity. P-values for these statistical tests will be provided for descriptive purposes. However, if a statistical test on a secondary outcome is significant at the 2-sided significance level of 0.01, the finding will be considered worthy of future investigation.

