L Post-op standard therapy, including adjuvant CT and RT, based on final pathologic stage of cancer, tumor margins, and other standard clinical criteria. Post-op therapy is non-study specific and can be given through the primary oncology team.

m Adjuvant Pembrolizumab: Patients who receive both adj CT plus adj RT should start Pembrolizumab within 8 months of surgery. Patients who receive only one modality of adj therapy (e.g. CT alone or RT alone) should start Pembrolizumab within 6 months of surgery. Patients who do not receive any adjuvant therapy should start Pembrolizumab within 4 months of surgery.

n Tumor Biopsy Slides (appendix I)

P Surgery to occur at 4-8 weeks (29-56 days). If dose # 2 pembrolizumab delayed, there is to be at least 2 days between this infusion and surgery. Tumor Specimen collection (appendices G & H)

R Post-Surgery F/U visit: Two to 6 weeks following surgery. Subjects with bulky residual adenopathy such that resection was not attempted will be removed from protocol therapy and should receive standard oncology care as deemed appropriate by the treating physician. Subjects with positive surgical margins or N2 disease will be removed from protocol and considered for standard of care post-operative radiation +/- standard chemotherapy as deemed appropriate by their physician. Subjects who are completely resected or who refuse or cannot receive adjuvant chemotherapy will be given the option of receiving adjuvant Pembrolizumab. Collection #3 research blood sample 2-6 weeks after surgery prior to initiation of adjuvant CT.

S End of Study Visit: End of study evaluation is to occur approximately 30 days or more after adjuvant Pembrolizumab treatment. SAEs will be collected for 90 days after the end of treatment. Final research blood sample will be collected (collection #4). Chest CT if applicable (per radiologic evaluation, Appendix A)

T Follow-Up: Patients should have follow-up every 3-4 months as per standard care (of the treating institution (recurrence and survival) for 2 years unless patients has experienced > grade 1 toxicity related to Pembrolizumab (in which case follow until resolution of the AE to Grade 0-1, patient deemed stable by investigator, or new anti-neoplastic therapy has begun.). After 2 years follow every 6 months for up to five years. These evaluations may be coordinated with visits for radiologic disease evaluation or occur via phone follow-up. Lab assessments will be at the discretion of treating physician.

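### Appendix A note T, as worded, replaces the two-year recurrence and survival follow-up for patients with related toxicity above grade 1, contradicting every other outcome follow-up rule in the plan

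*Combined protocol and SAP*

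**What the plan says.** Note T in Appendix A (29.1), labelled as follow-up and concerning recurrence and survival, prescribes a contact every 3-4 months "for 2 years unless patients has experienced > grade 1 toxicity related to Pembrolizumab (in which case follow until resolution of the AE". Resolution means grade 0-1; a judgement by the investigator that the patient is stable, or the start of new anti-neoplastic therapy, also ends it. Its next sentence reads "After 2 years follow every 6 months for up to five years" and carries no toxicity condition.

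The other outcome follow-up rules have no toxicity exception:

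- Section 9.8.6: "Outcome data (recurrence and survival) will be collected every 3-4 months for 2 years after surgery", then "Following that, collect follow-up every 6 months for up to five years".
- Section 4.1, with the same statement in 27.1: "eligible subjects (not screen failures) will be followed for 2 years for both disease recurrence and death".
- Section 27.1, accrual and follow-up: "All registered patients will be followed for tumor response, disease free survival and overall survival".
- Section 5.0 gives outcome follow-up of up to 7 years, in a statement separate from its rule on side effects.
- Section 19.3.3 moves patients who start new anti-cancer therapy into survival follow-up.

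Elsewhere, the AE-resolution wording governs AE follow-up only. In 9.8.5, patients with a related event above grade 1 "will be followed until the resolution of the AE to Grade 0-1, or investigator deems stable", with new therapy as a further end point. In 5.0, "follow-up will continue until pembrolizumab related side effects are grade 1, or Investigator deems stable".

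**The concern.** The construction in note T is one of replacement: a two-year schedule applies unless there was toxicity, and in that case a different end point applies. An adverse event can resolve well before two years are up. A coordinator who follows the note could stop collecting recurrence and survival data at that point, and only for patients who had related toxicity above grade 1.

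The length of observation would then depend on toxicity. DFS is a secondary objective, and secondary objective 3 fits logistic and Cox models of blood biomarkers against objective response, DFS and OS. Section 27.1 gives no censoring rule for DFS or OS, so the analysis plan does not protect against such a gap. If patients with toxicity differ in prognosis from the rest, the censoring is informative. If they do not, information is lost without bias.

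**Working it through.** **1. The rules side by side.** The plan states no DFS or OS target, so there is no design figure to reproduce on this point.

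| Place | Who | End of follow-up | Toxicity exception |
|---|---|---|---|
| 4.1, 27.1 | eligible subjects | 2 years, recurrence and death (27.1 adds six-monthly, up to five years) | none |
| 27.1, accrual | all registered patients | not stated; DFS and OS | none |
| 9.8.6 | patients | 3-4 monthly for 2 years after surgery, then six-monthly, up to five years | none |
| 5.0 | patients | up to 7 years for outcome | none |
| 15.1 | discontinued without progression | progression, non-study treatment, consent withdrawal, loss to follow-up | none |
| 19.3.3 | after new therapy | survival follow-up continues | none |
| Note T, first 2 years | related toxicity above grade 1 | AE resolved or stable, or new therapy | yes |
| Note T, after year 2 | patients | six-monthly, up to five years | none |

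Only the first-two-years part of note T makes toxicity an exception. It also treats new therapy as an end point, whereas 19.3.3 treats it as the start of survival follow-up.

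**2. Observation time at risk.** The documents give no rate of related toxicity above grade 1. Assume a share q of 10% to 40%, with follow-up stopping t = 1 to 12 months after surgery. The fraction of planned months lost within the 24-month window is q × (24 − t) / 24.

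- Smallest: 0.10 × 12/24 = 5%.
- Largest: 0.40 × 23/24 = 38%.

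If all 30 evaluable patients were resected, 30 × 24 = 720 planned person-months would fall to 684 and 444 respectively.

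**3. Possible bias in 24-month DFS.** Assume exponential DFS with a 36-month median in patients without toxicity, so S(t) = 2^(−t/36), and a hazard ratio h for patients with toxicity, so S_h(t) = 2^(−ht/36). Suppose patients with toxicity stop at time c and the gap is never filled. In large samples:

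- True value: (1 − q)·S(24) + q·S_h(24)
- Kaplan-Meier limit: [(1 − q)·S(c) + q·S_h(c)] × S(24 − c)

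Worked case, q = 0.4, h = 2, c = 3:

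- True: 0.6 × 0.630 + 0.4 × 0.397 = 0.537.
- Estimated: (0.6 × 0.944 + 0.4 × 0.891) × 0.667 = 0.616.
- Error: +7.9 points.

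| q | h | true | error, c = 3 | error, c = 12 |
|---|---|---|---|---|
| 0.1 | 0.5 | 0.646 | −1.5 points | −0.9 |
| 0.4 | 0.5 | 0.695 | −5.8 | −3.5 |
| 0.1 or 0.4 | 1 | 0.630 | 0 | 0 |
| 0.1 | 2 | 0.607 | +2.0 | +1.0 |
| 0.4 | 2 | 0.537 | +7.9 | +4.1 |

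A simulation at c = 3 gave the same errors to within about 0.1 point.

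**4. What these figures are.** They assume permanent censoring. Note T resumes contact after year 2, when deaths and many recurrences could be recovered, so for given q, h and c these figures overstate what the note implies. The residual risk is recurrences dated late and patients lost during the gap.

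**The case against.** The strongest reply is that the plan as a whole does not truncate anything. Sections 4.1, 5.0, 9.8.6 and 27.1 all require outcome follow-up regardless of toxicity. Section 5.0 is the most telling, because it states side-effect follow-up and outcome follow-up separately, which makes the first additional to the second. Section 9.0 describes Appendix A as a summary of procedures detailed in that section, and note g of the same appendix recommends chest CT every 3-4 months, or per institutional standard, for 2 years with no toxicity exception. This stands as evidence of intent. It does not remove the conflict: 15.1 sends sites to Appendix A and Section 9.0 together for follow-up procedures, and no rule says which prevails.

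A reader might infer that DFS and OS are in fact cut short by toxicity status. The documents do not support that, given the sections above and the resumption after year 2. Nor do they say that sites work from Appendix A in preference to Section 9.

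A reader might also infer that the protocol itself ties toxicity to prognosis. Sections 1.5 and 5.1.3 hypothesise only that blood biomarkers may be associated with response and/or autoimmune events; neither links toxicity to DFS or OS.

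The numerical inputs can also be challenged. Patients who complete adjuvant pembrolizumab could not reach the end of treatment one or three months after surgery, so early stopping times suit early discontinuers rather than completers. That stands, and it is why the 12-month column is shown.

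**Conclusion.** Wrong as written: note T contradicts the rest of the plan on who has recurrence and survival follow-up in the first two years. It is an internal contradiction in one footnote, not a deliberate choice to censor by toxicity.

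The exposure is a possible gap in outcome data up to month 24, confined to patients with related toxicity above grade 1, at any site that applies the note literally. If toxicity is unrelated to prognosis, only precision is lost. If it is related, the direction of bias depends on the direction of the relation. The size cannot be fixed from the documents: under the assumptions shown, with the gap never filled, the error in 24-month DFS is about 1 to 6 points too low at a hazard ratio of 0.5 and about 1 to 8 points too high at 2.

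Only secondary, exploratory endpoints are exposed: DFS, OS and the biomarker Cox models. Surgery feasibility, the primary endpoint, is unaffected.

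**What to change.** Reword note T so that all patients have recurrence and survival data collected on the 9.8.6 schedule whatever their toxicity, and so that patients with related toxicity above grade 1 are, in addition, followed for the event as 9.8.5 already provides. In practice, the exception becomes an addition. Reconcile the note's new-therapy end point with 19.3.3.

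Add one sentence to 27.1 stating that resolution or stabilisation of an adverse event is not a censoring event for DFS or OS.

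The cost is one footnote and one sentence. No visits are added, because 9.8.6 already plans this follow-up and allows it by phone. For any patient whose outcome contacts were stopped under the old wording, ask the site for the missing recurrence and survival dates.

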29.2 Appendix B- Correlative Science Measures

Correlative Science Primary Objective

Circulating T Lymphocytes with Specificity Against Tumor Associated Antigens:

Detectable circulating T cells with specificity against TAA will be identified using the following process:

Whenever individual patient tumor tissue is available for analysis, the expression of 10 highly conserved TAA's (see Table I below) will be assessed using standard Real-Time (RT) PCR technology. Peptide pools representing the three most highly expressed TAA's by each tumor will serve as antigen-specific stimulators for PBMC isolated from the same patient at the 4 specified time points. If no tumor tissue is available for TAA expression analysis, peptide pools representing the three most commonly expressed TAA's on NSCLC, namely Survivin, PRAME, and MAGE-A3, will be chosen as antigen-specific stimulators.

The percentage of CD4, CD8, and double positive (DP=CD4+/CD8+) lymphocytes with specificity against the three selected TAA's, will be calculated for each of 4 individual functional markers (IL-2, TNF- α , IFN- γ , and CD107 underlined below). For each peripheral blood collection, the lab will generate a total of 12 lymphocyte values (4 values each for CD4, CD8 and DP) for each of the three TAA's and for CD3/CD28 (used as a positive control), as well as generating 12 background unstimulated negative control values. All values will be expressed as percentages. A patient will be considered to have detectable circulating T cells if ≥ 1 of the 36 percentage values (12 values * 3 TAA's) satisfies the definition of "detectable" as described in section 26.0 (a lymphocyte percentage of $\geq 0.05\%$ at the pre-surgical peripheral blood collection (Collection 3) with each value also being at least twice that of the background unstimulated negative control value).

Table I **TAA Peptide Pools**
(15-mers, overlapping by 11 amino acids)

Survivin (33 peptides)
PRAME/OIP4 (125 peptides)
MAGE-A3 (76 peptides)
Melan A/MART-1 (27 peptides)
Gp100 (163 peptides)
Tyrosinase (117 peptides)
NY-ESO-1 (43 peptides)
MAGE-A1 (75 peptides)
MAGE-A4 (77 peptides)
CEA (173 peptides)

Assessing detectable circulating T cells specific against three TAA's (individually selected from the Table I list of TAA's using the process outlined above) in the following combinations of T cells and functional markers:

- * %**CD4**+/**CD69**+/**IL-2**+
- *%**CD4**+/**CD69**+/**TNF- α** +
- *%**CD4**+/**CD69**+/**IFN- γ** +
- *%**CD4**+/**CD69**+/**CD107**+

- * %**CD8**+/**CD69**+/**IL-2**+
- *%**CD8**+/**CD69**+/**TNF- α** +
- *%**CD8**+/**CD69**+/**IFN- γ** +
- *%**CD8**+/**CD69**+/**CD107**+

- * %**DP**+/**CD69**+/**IL-2**+
- *%**DP**+/**CD69**+/**TNF- α** +
- *%**DP**+/**CD69**+/**IFN- γ** +
- *%**DP**+/**CD69**+/**CD107**+

Exploratory Objectives

Tumor Infiltrating Lymphocytes with Specificity Against Tumor Associated Antigens:

Using the same methods noted above, 12 lymphocyte percentage values (functional markers) for the 3 selected TAA's will also be generated from tumor tissue collected at surgery, and in this context are called tumor infiltrating lymphocytes (TILs). These values will be used to determine the percentage of patients with any detectable TILs (exploratory objective 1). Expression percentage values for each T cell (CD4, CD8, and DP) will also be collected corresponding to each combination of the 4 functional markers (excluding the combination where all four markers are negative) using Boolean gating. These 135 values (15 values * 3 T cells * 3 TAA's) will be used to determine a definition of detectability suitable for these measures to avoid missing potential positive values, and to determine the percentage of patients with ≥ 1 of the 135 values satisfying the new definition of detectable circulating T cells (exploratory objective 5). In addition, this definition will also be used to explore whether the presence, quantity or quality of TILs is associated with pathologic response (exploratory objective 6).

* Boolean gating will be performed to calculate percentage values corresponding to the following combinations of T cells and functional markers (excluding the combination where all 4 markers are negative):

- * %**CD4**+/**CD69**+/**IL-2**+ or **TNF- α** + or **IFN- γ** + or **CD107**+ or -
- * %**CD8**+/**CD69**+/**IL-2**+ or **TNF- α** + or **IFN- γ** + or **CD107**+ or -

* %**DP**+/**CD69**+/-**IL-2**+ or -**TN α** + or -**IFN- γ** + or -**CD107**+ or –

For exploratory outcome 4, changes in all measures of anti-TAA reactivity listed below across time points will be analyzed, as well as how these values relate to pathologic response. In addition, for the phenotypic reactivity measures with background unstimulated negative control values (those from the ICS panel), the percentage of patients with a positive response (a percentage value greater than the background unstimulated negative control value) will be calculated. The distribution of the changes will be estimated with a boxplot and the median (mean) change will be calculated by pathologic response status (yes/no).

%**CD3**+**CD4**+**CD8**- (CD4 T cells)

%**CD3**+**CD4**-**CD8**+ (CD8 T cells)

%**CD3**+**CD4**+**CD8**+ (CD4/CD8 double positive (DP) T cells)

%**CD4**+**CD152**- (CTLA-4 negative CD4 T cells)

%**CD4**+**CD152**+ (CTLA-4+ CD4 T cells)

%**CD4**+/**CD69**+ (Activated CD4 T cells)

%**CD4**+**CD154**+ (Activated CD4 T cells)

%**CD4**+/-**HLA-DR**+ (Activated CD4 cells)

%**CD4**+**CD28**+

%**CD4**+**CD28**-

%**CD4**+/**CD28**+/**CD152**+**CD279**+ (Activated/Exhausted CD4 T cells)

%**CD4**+**CD28**+**CD278**+ (Activated CD4 T cells/Pharmacodynamic Biomarker)

%**CD4**+/**CD25**+**FoxP3**+/**CD152**

%**CD4**+/**CD25**+**FoxP3**+/**CD152**

%**CD4**+/**CD25**+**FoxP3**+/**CD152**

%**CD4**+/**CD25**+**FoxP3**+/**CD152**

%**CD4**+**CD45RA**+**CCR7**+ (Naïve CD4 T cells)

%**CD4**+**CD45RA**-**CCR7**+ (Central memory CD4 T cells)

%**CD4**+**CD45RA**-**CCR7**- (Effector memory CD4 T cells)

%**CD4**+**CD45RA**+**CCR7**- (Effector CD4 T cells)

%**CD8**+**CD152**- (CTLA-4 negative CD8 T cells)

% **CD8**+**CD152**+ (CTLA-4 positive CD8 T cells)

%**CD8**+**CD69**+ (Activated CD8 T cells)

%**CD8**+**CD152**+ (Activated CD8 T cells)

%CD8+/-HLA-DR+ (Activated CD8 T cells)
%CD8+CD28+
%CD8+CD28-
%CD8+/CD28+/CD152+CD279+ (Activated/Exhausted CD8 T cells)

%CD8+CD45RA+CCR7+ (Naïve CD8 T cells)
%CD8+CD45RA-CCR7+Central memory CD8 T cells)
%CD8+CD45RA-CCR7- (Effector memory CD8 T cells)
%CD8+CD45RA+CCR7- (Effector CD8 T cells)

%DP CD69+ (Activated DP T cells)
%DP CD154+ (Activated DP T cells)

%DP CD45RA+CCR7+ (Naïve DP T cells)
%DP CD45RA-CCR7+ (Central memory DP T cells)
%DP CD45RA-CCR7- (Effector memory DP T cells)
%DP CD45RA+CCR7- (Effector DP T cells)

%CD3-SSC^{hi}/HLA-DR^{low}CD14⁺ (Myeloid-derived suppressor cells (MDSC))
FCSxSSC (Monocyte gate)%CD3-CD14- Lin(CD16, CD19, CD20, CD56)- HLA-DR-
CD11b+/CD33+ (MDSC)

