17.5 Pathologic Response Criteria

After receiving preoperative pembrolizumab, criteria for examining resected tumor will be as follows:

- No Response: no evidence of cell death or tumor necrosis.
- Partial Response: $\geq 30\%$ tumor necrosis or cell death.
- Complete Response: no evidence of viable tumor in surgical specimen (includes lung tissue and dissected lymph nodes)

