- 9) Determine if the immunomodulatory effects of neoadjuvant chemotherapy plus pembrolizumab impact the suppressive mechanisms, restoring functional reactivity to important anti-tumor effector cell populations. Functional TAA-specific T cell reactivity’s will be measured in the blood at 4 time points: Collection 1, 2, 3 and 4. A Wilcoxon rank sum test will be used to test for differences from baseline, as well as for any association between each reactivity measure and pathologic response to neoadjuvant therapy.
- 10) Explore an alternative definition for detectability suitable for expression values generated using Boolean gating, and determine the percentage of patients with circulating T cells meeting this definition. The percentage of patients with circulating T cells meeting the new definition of detectable and its 95% exact confidence interval.
- 11) Perform gene expression analysis on tumor to elucidate genes associated with function and modulation of the PD-1/PD-L1 axis.

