29.8 Appendix H-Tissue Specimens-Duke

Surgical Tissue Specimen for Correlative Sciences Duke Processing

SURGICAL SPECIMEN

Patients will be approached to participate in the “DUHS Biospecimen Repository and Processing core BRPC eIRB 35974” protocol prior to surgery. Tissue will be collected and released as described in this protocol to ensure proper involvement of pathology to minimize the chance that a tissue collection event interferes with appropriate clinical tissue processing and diagnosis.

PRINCIPLE: Lung tissue is harvested in the frozen section or gross dissection area of the surgery pathology suite. The tissue is first examined by a certified anatomic pathologist or surrogate (resident, pathology assistant). Relevant margins are inked, removed and examined by frozen section analysis, if necessary. It is imperative that harvesting tissue for use in research trials does not impeded accurate initial assessment of critical features of the tumor resection, most notable margin status. After the specimen has been processed for margin status, the frozen section assessment of the specimen is complete, a specimen of excess tumor will be released and acquired by the tumor immunology correlative science staff for isolation of tumor infiltrating lymphocytes (TILs) for purposes of this protocol (as much tissue as possible, but a minimum 1 gm).

SPECIMEN: Lung resection specimen

LOCATION: Surgical Pathology Suite

QUALITY CONTROL: Lab guidelines for safe handling of all samples must be followed. All tubes used for specimen processing must be labeled with the unique patient identifier or sample number before transfer of the tissue sample.

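### Antigen panel for the T-cell assay depends on tumour-tissue availability, which is linked to pathologic response, and item 9 compares responders with non-responders without regard to panel

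*Combined protocol and SAP*

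**What the plan says.** Appendix B (29.2) sets two rules for the peptide pools used on blood T cells.

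- **Matched panel.** The condition is "Whenever individual patient tumor tissue is available for analysis". Ten antigens are then typed by RT-PCR, and "Peptide pools representing the three most highly expressed TAA's by each tumor will serve as antigen-specific stimulators for PBMC isolated from the same patient", at all four blood draws.
- **Default panel.** "If no tumor tissue is available for TAA expression analysis, peptide pools representing the three most commonly expressed TAA's on NSCLC" are used instead, "namely Survivin, PRAME, and MAGE-A3, will be chosen as antigen-specific stimulators".

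Appendix B does not say which tissue is typed or when it was taken. Sections 9.5 and 10.2 and Appendices H and I describe research tumour as excess tissue released at resection, after the neoadjuvant doses. Appendix H asks for "as much tissue as possible, but a minimum 1 gm", a minimum set for isolating TILs. Screening (Section 9.1) lists tumour histology but no research tumour sample. The study schedule has a row for tumour biopsy slides, marked under Surgery and referred to Appendix I, which as supplied does not describe them.

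Section 17.5 defines pathologic complete response as "no evidence of viable tumor in surgical specimen". Item 9 of the secondary objectives (Sections 4.2 and 27.1) uses a Wilcoxon rank sum test for "any association between each reactivity measure and pathologic response to neoadjuvant therapy". Appendix B also summarises changes by pathologic response status. Neither place records or adjusts for the panel used.

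**The concern.** A patient assayed with matched antigens and a patient assayed with the default trio have had different tests. That adds only noise if panel type is unrelated to the outcome. Here it is plausibly related: a specimen without viable tumour offers little or nothing to type, so complete responders are the resected patients most likely to receive the default trio.

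The plan prefers matched antigens whenever it can use them, which suggests that it expects them to be more informative. If so, responders would read low for technical reasons, and a true positive association with response would be hidden or reversed. If the default trio were the more sensitive panel, the error would run the other way.

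Appendix B calls circulating antigen-specific T cells its primary correlative objective, and item 9 is where that reactivity is set against response. A result at the two-sided 0.01 level counts as worth pursuing, so a panel artefact could steer later work.

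**Working it through.** The plan gives no figure for this effect, so there is none to reproduce. Its value count is consistent: 12 values x 3 antigens = 36 per blood collection.

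**1. Which analyses are exposed**

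| Analysis | Exposed to panel type? | Reason |
|---|---|---|
| Item 9, stimulated reactivity vs pathologic response | Yes | Between-patient comparison; panel can differ by response |
| Appendix B changes, by response status | Yes, for stimulated measures | A less sensitive panel can shrink the change itself |
| Item 9, change from baseline within a patient | Protected from a panel switch | Same panel at all four draws |
| Unstimulated phenotypes in Appendix B | No | No antigen stimulation |
| Item 5, TILs vs pathologic response | No | A TIL value already requires surgical tumour |
| Primary endpoint | No | Assay not used |

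**2. Effect on a detected proportion**

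Let f_R and f_N be the shares of responders and non-responders on the default panel, and p_m and p_d the detection rates with the matched and default panels. With no true association:

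spurious difference = (f_R - f_N) x (p_d - p_m)

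All four inputs are assumptions. With f_N = 0:

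| f_R | p_m = 60%, p_d = 30% | p_m = 60%, p_d = 50% |
|---|---|---|
| 10% | -3 points | -1 |
| 25% | -7.5 | -2.5 |
| 50% | -15 | -5 |
| 100% | -30 | -10 |

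For f_R of 25-50%, p_m of 50-70% and p_d of 30-50%, the extremes are:

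- smallest: p_m = p_d = 50%, so f_R x 0 = 0;
- largest: 0.50 x (0.30 - 0.70) = -20 points.

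If non-responders also lack tissue, the difference shrinks. With f_R = 50%, f_N = 25% and 60% vs 30% detection, it is 0.25 x (-0.30) = -7.5 points.

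**3. Effect on the rank sum test**

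The plan's historical surgery rate of about 80%, applied to 30 evaluable patients, gives 24 resected. Assume 8 responders, no true association, and a default panel that lowers the reading by 0.5 or 1 SD. Two-sided false-positive rates from 3,000 simulated trials per row:

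| Responders on default | Shift | At 0.05 | At 0.01 |
|---|---|---|---|
| 2 of 8 | 0.5 SD | 5.0% | 1.2% |
| 4 of 8 | 0.5 SD | 6.3% | 1.3% |
| 8 of 8 | 0.5 SD | 18.3% | 6.5% |
| 2 of 8 | 1 SD | 7.0% | 1.7% |
| 4 of 8 | 1 SD | 15.8% | 4.7% |
| 8 of 8 | 1 SD | 55.6% | 29.0% |

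With no panel shift, the rates across all simulated settings were 4.0-5.3% at 0.05 and 0.5-1.0% at 0.01. Simulation error is about 0.4 points at 5% (square root of 0.05 x 0.95 / 3,000).

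**The case against.** Much can fairly be said against a strong version of this point.

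- **Source of tissue.** A reader might infer that response decides the panel and that complete responders always get the default. Appendix B speaks only of available tumour tissue, so a diagnostic biopsy is not excluded. Tissue can also be missing for reasons unrelated to response: clinical pathology takes priority for it, and outside sites may not ship from Thursday to Sunday. This stands: the link is a likelihood, not a rule.
- **The 1 g minimum.** It is tempting to conclude that partial responders with little residual tumour also lose the matched panel. The minimum is for TIL isolation, not RT-PCR. Partial response needs only 30% necrosis or cell death, and the 3 cm entry requirement is there to secure tissue.
- **Unresected patients.** A reader might expect them to create a false link with good outcome. They have no surgical specimen to grade and no DFS, which runs from resection, so they do not enter the pathologic-response comparison.
- **Items 3 and 5.** Item 5 needs surgical tumour anyway. Item 3 concerns blood-based biomarkers, and Sections 1.5 and 5.1.3 describe blood profiling as circulating cytokines. The documents do not show that it covers stimulated reactivity.
- **Coincidence of panels.** The default antigens are described as the commonest on NSCLC and may match a patient's own top three.
- **Stakes.** All secondary objectives are exploratory, with descriptive p-values.

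These arguments narrow the point to item 9 and the summaries by response. They do not remove it: the tissue source is unstated, the one described collection is after treatment, and no record of panel type is planned.

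**Conclusion.** The concern holds for TAA-stimulated blood reactivity compared between pathologic responders and non-responders. Panel type is likely to be associated with response, and the planned comparison does not separate a difference in assay from a difference in biology.

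The size cannot be established from the documents. Under the assumed ranges it is 0 to -20 percentage points in a detected proportion. The rank sum test stays near nominal when 2 of 8 responders are on the default panel with a 0.5 SD shift, and is seriously inflated only when many responders are on it and the panels differ substantially. The negative sign assumes that matched antigens detect more. If few responders lack typable tissue, or the panels perform alike, the effect is negligible.

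This is an inexpensive correction to an exploratory analysis. It does not bear on the trial's primary conclusion.

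**What to change.** In Appendix B and in item 9 (Sections 4.2 and 27.1):

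1. State the source and date of the tissue used for antigen typing. Where pre-treatment diagnostic tissue already exists, use it, so that panel choice does not depend on response. Section 6.2 also accepts cytologic diagnosis, so this will not cover everyone and steps 2 to 4 are still needed.
2. Record panel type (matched or default) for every patient.
3. Stratify the test of stimulated reactivity against pathologic response by panel type, for example with a van Elteren test, and show the Appendix B summaries by panel within response group.
4. Report matched-panel patients alone as well.

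The cost is one data field and a few lines of text, plus some precision. A default stratum that holds only responders contributes no comparison, so those patients drop out of a test on about 24. The matched-panel analysis then says little about complete responders, and the report should say so.

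Using the fixed trio in all patients would also remove the problem, and the number of assays would not change. It gives up patient-specific antigens and some sensitivity where a tumour does not express the trio. That is a scientific choice for the sponsor, not a required correction.
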